6. ADVERSE EVENTS: LIST AND REPORTING REQUIREMENTS

6.1 Study Drugs

6.1.1 Entinostat

Commonly encountered AEs across clinical studies of entinostat monotherapy in patients with solid tumors included hypoalbuminemia, fatigue, nausea, hypophosphatemia, anemia, and thrombocytopenia. Incidence and severity were dose- and schedule-dependent. In a Phase 2, randomized, placebo-controlled study in patients with lung cancer, in which patients received erlotinib+entinostat or erlotinib+placebo, treatment-emergent adverse events (TEAEs) occurring at a $\geq 10\%$ higher incidence in entinostat-treated patients versus placebo-treated patients included nausea (49% versus 25%); anorexia (40% versus 16%); weight decreased (32% versus 18%); dyspnea (31% versus 18%); vomiting (31% versus 13%); peripheral edema (28% versus 13%); anemia (22% versus 11%); thrombocytopenia (15% versus 3%); hypotension (14% versus 2%); and stomatitis (12% versus 2%). In a Phase 2 study in patients with metastatic melanoma treated with entinostat monotherapy, the most common TEAEs were nausea (39%), hypophosphatemia (29%), pain in extremity (21%), and back pain and diarrhea (each 18%) [122]. Additional clinical experience is summarized in the entinostat IB.

6.1.2 Nivolumab

Blocking PD-1 function may permit the emergence of auto-reactive T cells and resultant clinical autoimmunity. Rash/pruritus, diarrhea/colitis, pneumonitis, hepatitis, and hypothyroidism were drug-related, presumptive autoimmune events noted in previous nivolumab studies.

For the purposes of this study, a nivolumab-related AE is defined as an AE of unknown etiology, associated with drug exposure and is consistent with an immune phenomenon. Efforts should be made to rule out neoplastic, infectious, metabolic, toxin or other etiologic causes. Serological, immunological, and histological (biopsy) data should be used to support the diagnosis of an immune-mediated toxicity. Suspected nivolumab-related AEs must be documented on an AE CRF. Identification and treatment of nivolumab-related AEs can be found in **Section 4.4** as well as in **Appendix D**. Additional guidance can be found in the nivolumab IB.

6.2 Adverse Events Definition

6.2.1 Adverse Events

An AE is defined in the International Conference on Harmonisation (ICH) Guideline for Good Clinical Practice as "any untoward medical occurrence in a patient or clinical investigation patient administered a pharmaceutical product and that does not necessarily have a causal relationship with this treatment" (ICH E6:1.2).

Worsening of a pre-existing medical condition, (e.g., diabetes, migraine headaches, gout) should be considered an AE if there is either an increase in severity, frequency, or duration of the condition or an association with significantly worse outcomes.

Interventions for pretreatment conditions (e.g., elective cosmetic surgery) or medical procedures that were planned before study enrollment are not considered AEs.

Disease progression (PD) should not be recorded as an AE. If PD occurs, record the date first documented in the EOT visit eCRF. Also record all methods of assessment, e.g., 1 target/nontarget lesion, tumor response assessment, and/or clinical disease assessment. Indicate if the patient starts new treatment.

In the case of death, only record "Fatal" for the event causing death. AEs that are ongoing at the end of the study or time of death are to be noted as "continuing."

Classification of AEs is to be done by the Investigator is according to the NCI CTCAE, Version 4.03. The Death eCRF must also be completed.

The Investigator is responsible for reviewing laboratory test results and determining whether an abnormal value in an individual patient represents a significant change from baseline. In general, abnormal laboratory findings without clinical significance (based on the Investigator's judgment) should not be recorded as AEs; however, laboratory value changes requiring therapy or adjustment in prior therapy are considered AEs.

6.2.2 Suspected Adverse Reactions

A suspected adverse reaction is any AE for which there is a reasonable possibility that the drug caused the adverse event. For the purposes of Investigational New Drug Application (IND) safety reporting, 'reasonable possibility' means there is evidence to suggest a causal relationship between the drug and the AE. A suspected adverse reaction implies a lesser degree of certainty about causality than adverse reaction, which means any AE caused by a drug.

6.2.3 Expectedness

Unexpected AE: An AE, which varies in nature, intensity or frequency from information on the investigational drug/agent provided in the product IB, package insert or safety reports. Any AE that is not included in the IB consent is considered "unexpected".

Expected (known) AE: An AE, which has been reported in the IB. An AE is considered "expected", only if it is included in the IB document as a risk.

6.2.4 Serious Adverse Events

An AE or suspected adverse reaction is considered "serious" if, in the view of either the Investigator or Sponsor, it results in any of the following outcomes:

- is fatal
- is life-threatening (e.g., places the patient at immediate risk of death)
- requires in-patient hospitalization or prolongation of existing hospitalization for >24 hours
- results in persistent or significant disability/incapacity

- is a congenital anomaly/birth defect
- is an important medical event that may not result in death, be life-threatening, or require hospitalization but may be considered a serious adverse drug experience when, based upon appropriate medical judgment, it may jeopardize the patient and may require medical or surgical intervention to prevent one of the outcomes listed in this definition. Examples of such medical events include allergic bronchospasm requiring intensive treatment in an emergency room or at home, blood dyscrasias or convulsions that do not result in inpatient hospitalization, or the development of drug dependency or drug abuse.
- Potential drug induced liver injury (DILI) is also considered an important medical event.
- Hemophagocytic lymphohistiocytosis is also considered an important medical event.
- Suspected transmission of an infectious agent (eg, pathogenic or nonpathogenic) via the study drug is an SAE.
- Is a new cancer (that is not a condition of the study)
- Is associated with an overdose
- Is a pregnancy or pregnancy outcome of spontaneous abortion, missed abortion, benign hydatidiform mole, blighted ovum, fetal death, intrauterine death, miscarriage, or stillbirth.

A hospitalization meeting the regulatory definition for "serious" is any in-patient hospital admission that includes a minimum of an overnight stay in a health care facility. Any AE that does not meet one of the definitions of serious (e.g., emergency room visit, out-patient surgery, or requires urgent investigation) may be considered by the Investigator to meet the "other significant medical hazard" criterion for classification as a serious adverse event (SAE).

6.3 Reporting Procedures for All Adverse Events

The Investigator is responsible for ensuring that all AEs observed by the Investigator or reported by patients are properly captured in the patients' medical records and reported on the eCRF. The evaluation time period for all adverse events is from the first dose of the investigational agent to at least 30 days after the last dose of entinostat or nivolumab, or until resolution of all acute toxicities associated with study drug administration, whichever is longer, with the exception of SAEs, which must be documented through 100 days following cessation of treatment, or 30 days after the initiation of a new anticancer therapy, whichever is earlier.

The following AE attributes must be assigned by the Investigator:

• event description (with detail appropriate to the event);

- seriousness;
- dates of onset and resolution;
- severity;
- assessment of relatedness to entinostat and to nivolumab; \Box the action taken.

Laboratory abnormalities: Laboratory abnormalities present at the screening visit will be recorded as pre-treatment signs and symptoms. After study treatment administration, all grade 3 and 4 clinical laboratory results that represent an increase in severity from baseline will be reported as AEs. A grade 1 or 2 clinical laboratory abnormality should be reported as an AE only if it is considered clinically significant by the investigator (induce clinical signs or symptoms or require therapy)

The Investigator may be asked to provide follow-up information, discharge summaries, and extracts from medical records.

If applicable, the study drug relationship will be assessed by means of the question: "Is there a reasonable possibility that the event may have been caused by one of the two drugs based on mechanism of action and/or toxicity profile, or by the combination of entinostat with nivolumab?" The relationship of an AE to the administration of the study drug is to be assessed by the investigator according to the following definitions:

- No (unrelated, not related, no relation): The time course between the administration of study drug and the occurrence or worsening of the adverse event rules out a causal relationship and another cause (concomitant drugs, therapies, complications, etc.) is suspected.
- Yes (related): The time course between the administration of study drug and the occurrence or worsening of the adverse event is consistent with a causal relationship and no other cause (concomitant drugs, therapies, complications, etc.) can be identified.

The following factors should also be considered:

• The temporal sequence from study drug administration - The event should occur after the study drug is given. The length of time from study drug exposure to event should be evaluated in the clinical context of the event.

- Underlying, concomitant, intercurrent diseases Each report should be evaluated in the context of the natural history and course of the disease being treated and any other disease the subject may have.
- Concomitant medication The other medications the subject is taking or the treatment the subject receives should be examined to determine whether any of them might be recognized to cause the event in question.
- Known response pattern for this class of study drug Clinical and/or preclinical data may indicate whether a particular response is likely to be a class effect.
- Exposure to physical and/or mental stresses The exposure to stress might induce adverse changes in the recipient and provide a logical and better explanation for the event.

The pharmacology and pharmacokinetics of the study drug - The known pharmacologic properties (absorption, distribution, metabolism, and excretion) of the study drug should be considered.

Whenever possible, the CTCAE, Version 4.03, should be used for assessing the severity of AEs (http://evs.nci.nih.gov/ftp1/CTCAE/CTCAE_4.03_2010-06-4_QuickReference_8.5x11.pdf).

For AEs that are not adequately addressed in the NCI CTCAE, the standard severity grading scale may be used (*Table 6.3.1*).

Grade	Standard Adverse Event Severity Scoring System								
1	Mild:	Aware of sign or symptom, but easily tolerated.							
2	Moderate:	Discomfort enough to cause interference with usual activity.							
3	Severe:	Incapacitating with inability to work or do usual activity.							
4	Life-Threatening	S: Refers to an event in which the patient was, in the view of the Investigator, at risk of death at the time of the event. (This category is not to be used for an event that hypothetically might have caused death if it were more severe.)							
5	Fatal:	Event resulted in death.							

Table 6.3.1Standard Severity Grading Scale

It will be left to the Investigator's clinical judgment to determine whether an AE is related and of sufficient severity to require the patient's removal from treatment or from the study.

A patient may also voluntarily withdraw from treatment due to what he/she perceives as an intolerable AE. If either of these situations arises, the patient should be strongly encouraged to undergo an end-of-study assessment and be under medical supervision until symptoms cease or the condition becomes stable.

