4.10 Duration of Follow Up

The Follow-Up Phase begins when the decision to discontinue a subject from study therapy is made (no further treatment with study therapy).

All subjects who discontinue investigational product should comply with protocol specified follow-up procedures as outlined in Section 10, Study Calendar.

A mandatory End of treatment (EOT) visit (+/- 7 days) should be performed 28 days after the last dose of study drug(s).

After completion of the EOT visit, subjects will be followed every 3 months for survival.

Subjects who are discontinued from the study treatment due to an unacceptable toxicity will be monitored for safety until the resolution of the AE to \leq grade 1 or stabilization or until initiation of a new therapy for their cancer, whichever occurs first.

SAEs will be collected and recorded throughout the study period, from the first dose of the investigational agent through 100 days (+ 14 days) after the last dose of study drug or end of the study (if thought to be related to study drug), or 30 days after the initiation of a new anticancer therapy, whichever is earlier.

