6.4 Serious Adverse Event Reporting Procedures

SAEs will be collected and recorded throughout the study period, from the first dose of the investigational agent through 100 days after the last dose of study drug or end of the study (if thought to be related to study drug), or 30 days after the initiation of a new anticancer therapy, whichever is earlier.

All SAEs, regardless of causality to study drug and/or administration device, will be

promptly	to	the	IND	sponsor ai	nd BMS		Syndax	
reported								

within 24 hours of discovery or notification of the event.

Initial SAE information and all amendments or additions must be recorded on a Serious Adverse Event Report Form and provided to Syndax and BMS or their representative. The SAE reporting procedure is provided in **Appendix F**. If this falls on a weekend or holiday, an email notification is acceptable but must be followed by an SAE reporting form on the next business day.

After the initial SAE report, the investigator is required to proactively follow each subject and provide further information to the safety department in regards to the subject's condition. All SAE(s) will be followed until:

- Resolution
- The condition stabilizes
- The event is otherwise explained
- The subject is lost to follow-up
- Death

As soon as relevant information is available, a follow-up SAE report will be submitted to the IND Sponsor, BMS, and Syndax.

For all deaths, available autopsy reports and relevant medical reports should be provided to the IND Sponsor, Syndax and BMS or their representative. If a patient is permanently withdrawn from the study because of an SAE, this information must be included in the initial or follow-up Serious Adverse Event Report Form as well as the EOT eCRF.

The Investigator should notify the IRB or EC of SAEs occurring at the site and other AE reports received from Syndax and BMS, in accordance with local procedures and statutes.

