Such biopsies can be safely performed as evidenced by literature reports [122, 123], as well as, in the prior experience of our PI at the NIH Clinical Center [124], where, among 244 research tumor biopsies (18G needle) in liver (126), subcutaneous/chest wall/abdominal wall (36), intramuscular (18), lung and lymph nodes, there were 8 minor cases of bleeding, and one pneumothorax requiring 48h hospitalization (21). This evidence support that serial percutaneous core-needle biopsies can be obtained safely yielding material applicable for multiple translational applications.

Considering the tumor histologies to be enrolled in this study are pancreatic cancer and cholangiocarcinoma, biopsies will probably be of liver. In our institution, the expected complication rate of percutaneous liver biopsy similar to those that will be done for this trial is less than 1 %. Risks of the procedure include, but are not limited to, bleeding, infection, pain, and scarring.

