Female subject of childbearing potential should have a negative urine or serum pregnancy test within 72 hours prior to receiving retreatment with study medication. NOTE: If a patient has a positive or indeterminate serum or urine pregnancy test, then an ultrasound must be done to rule out pregnancy to enroll on trial. A serum B-HCG value of <25 is considered a negative pregnancy test.

- ^{14.} Radiologic imaging of chest/abdomen/pelvis (CT preferred, abdominal/pelvis MRI will be performed for patients with CT contrast allergy) and any other imaging required per RECIST for the particular subject are required at baseline. A baseline bone scan or PET/CT could be required to assess bone disease in patients with suspected or known bone metastases. A baseline brain CT scan or MRI is requested in patients with suspected or known brain metastases. Repeat same modality(ies) in follow-up to follow known site(s) of disease, with other assessments as clinically indicated if one has not been done within the past 6 weeks.
- ^{15.} Entinostat is to be self-administered by the patient weekly.
- ^{16.} Patients will receive entinostat 5 mg oral once a week plus nivolumab 240 mg every two weeks for approximately four months. After 4 months (16 weeks), nivolumab will be given at a dose of 480 mg fixed dose every 4 weeks. Therapy may continue with entinostat 5 mg weekly plus nivolumab 480 mg every 4 weeks, until intolerance or progression.

- ^{17.} Blood for serum and plasma samples will be collected at baseline (D -14), after entinostat lead in (on approximately day 14 (D-1) of entinostat therapy), on week 6, prior to dosing on C2D15, and at the time of the EOT visit. Detailed instructions for blood collection, processing, and storage are provided in the Laboratory Manual.
- ^{18.} Mandatory fresh tissue samples will be collected at D-14 and after entinostat lead-in (on approximately day 14 (D-1) of entinostat therapy prior to dosing on C1D1) and on week 6, prior to dosing on C2D15. A ± 3 day window applies to both time points. All

J1798/Version 5.0/May 21, 2020

samples are collected pre-dose on treatment days). Approximately six (6) core biopsy specimens will be obtained with each biopsy as outlined; the cytopathology slide will also be retained and submitted, if performed (See Section 9.2.1) All

correlative blood/tissue studies should be performed on the same day.

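### Complications of the mandatory baseline research biopsy that begin before the first dose have no required AE or SAE reporting route, and patients biopsied but never dosed fall outside the safety set.

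*Combined protocol and SAP*

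**What the plan says.** **Collection windows.** Section 6.3 states: "The evaluation time period for all adverse events is from the first dose of the investigational agent". Section 6.4 says of serious events: "SAEs will be collected and recorded throughout the study period, from the first dose of the investigational agent through 100 days after the last dose". Section 4.10 uses the same start, "from the first dose of the investigational agent through 100 days (+ 14 days) after the last dose of study drug". The sections word the end of the window differently, but all three open it at the first dose.

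**Analysis sets.** Section 8.2 counts toxicity from first treatment. Sections 8.4 and 12.3.2 limit the safety analysis to patients who have received study drug.

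**The biopsy.** Study Calendar footnote 18 says: "Mandatory fresh tissue samples will be collected at D-14 and after entinostat lead-in". It adds that "samples are collected pre-dose on treatment days" and allows a window of 3 days either way. Footnote 1 places biopsies after eligibility is established and the patient is registered. Day -14 is also the day of the first entinostat dose. A third mandatory biopsy follows at week 6 from Cycle 1 Day 1.

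**Expected harm.** Section 9.2.1 names bleeding, infection, pain and scarring as risks and puts the institution's complication rate for comparable liver biopsies below 1%. It also cites a series of 244 research biopsies in which "there were 8 minor cases of bleeding, and one pneumothorax requiring 48h hospitalization".

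**The concern.** The baseline biopsy is mandatory and done for research, and the patient is on study when it happens. The rule that opens safety reporting depends on a dose that has not yet been given. If the rule is followed exactly, a bleed or pneumothorax that begins after the biopsy and before the first capsule or tablet need not be entered as an AE or reported as an SAE.

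The most serious case is a patient whose complication prevents treatment from starting. That patient never enters the reporting window and never joins the safety set. The Safety Monitoring Committee, which reviews safety data at least twice a year (section 12.3.3), could then have an incomplete view of harm from a procedure that the protocol itself imposes.

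There is a smaller analytic cost. Section 6.1.1 lists thrombocytopenia among the common entinostat events. A dated record of bleeding before the first dose would help to separate biopsy harm from drug harm later.

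**Working it through.** There is no plan figure to reproduce, since the point concerns reporting rules. The check has two parts.

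**1. Timeline**

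| Event | Timing | Inside the AE/SAE window? |
|---|---|---|
| Registration | Before any biopsy | No |
| Biopsy 1 | Day -14, pre-dose, 3-day window either way | No, for onset before the first dose |
| First entinostat dose | Day -14 | Window opens |
| Biopsy 2 | About day 14 of entinostat | Yes |
| Biopsy 3 | Week 6 from Cycle 1 Day 1 | Yes |

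The gap can be hours, if biopsy and dose fall on the same day, or a few days, if the biopsy is early. It has no end if the dose is never given.

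Other provisions that might close the gap:
- Section 6.3 first asks the investigator to record all observed or reported AEs, but its next sentence limits the period to after the first dose.
- Section 6.4 requires 24-hour SAE reporting whatever the cause, but under the same first-dose start.
- Section 6.3 asks for relatedness to the two drugs only. The Appendix F form offers entinostat, nivolumab and underlying disease. Neither has a procedure item.
- The calendar row for symptom and toxicity assessment, as it can be read here, is blank at Baseline and Day -14 and starts at Day -7. The table may not have been extracted cleanly, so little weight rests on this.

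None of these requires an AE or SAE report for an event with pre-dose onset. A pneumothorax with 48 hours in hospital, as in the cited series, would meet the protocol's own seriousness criterion in section 6.2.4 (hospitalisation beyond 24 hours), yet before the first dose it would not have to be reported.

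**2. Scale**

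Inputs: n = 54 (27 × 2) to 66 (33 × 2), from section 12.2, assuming one baseline biopsy per patient. The rates p come from section 9.2.1: 1% as the ceiling of the under-1% statement; (8 + 1)/244 = 3.7% for any event; and 1/244 = 0.4% for a hospitalised event.

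Expected count = n × p. Chance of at least one = 1 − (1 − p)^n.

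| p | Expected, n = 54 | Expected, n = 66 | Chance of at least one |
|---|---|---|---|
| 1% | 0.54 | 0.66 | 42% to 48% |
| 9/244 | 1.99 | 2.43 | 87% to 92% |
| 1/244 | 0.22 | 0.27 | 20% to 24% |

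These count baseline-biopsy complications of any onset. Uncaptured events equal these counts times the share with pre-dose onset. The documents do not give that share, so it ranges from 0 to 100%.

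The counts also assume that both cohorts pass stage 1. Section 12.2 gives a 51% chance that a cohort stops at 13 if its true response rate is 5%. If both stop, n = 26, and at 1% the expected count is 0.26 with a chance of at least one of 1 − 0.99^26 = 23%.

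**The case against.** Starting AE collection at the first dose is a familiar drug-safety convention, and the protocol applies it consistently. The primary endpoint is unaffected. The unmonitored interval is short for anyone who goes on to be dosed, and bleeding, infection or pain that starts or worsens after the dose is reportable. All of this stands, and it limits the point to pre-dose onset and to patients never dosed.

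Other records exist. Section 4.8 requires the reason for and date of study removal on the case report form. Sections 6.4 and 6.9 refer to local IRB reporting procedures, and the weekly meetings in section 11.4 cover participant safety without restriction to dosed patients. So it would be wrong to say that such a patient leaves no trace. What is missing is a required AE or SAE entry and a place in the safety tables.

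Three stronger readings are tempting, but the documents do not support them:
- A reader might infer that baseline-biopsy complications as a whole go unrecorded. Only those with pre-dose onset lack a required route.
- A reader might infer that the under-1% rate cannot be checked. Biopsies 2 and 3 fall inside the window, giving up to 108 (2 × 54) to 132 (2 × 66) monitored procedures, so it can be checked in part.
- A reader might take 42% to 92% as the chance of an uncaptured event. It is the chance of any baseline-biopsy complication at rates of 1% to 3.7%. The low end is itself a ceiling for n = 54 under the stated rate, and the high end uses a mixed-site series in which 8 of 9 events were minor bleeds.

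Nor is the biopsy the only mandatory research procedure at Day -14, since research blood is drawn then too.

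**Conclusion.** The concern holds in a narrow form. AE and SAE collection opens at the first dose, the mandatory baseline biopsy comes before it in registered patients, and no section requires a report of a complication that begins in between. Patients biopsied but never dosed are outside both the reporting window and the safety set.

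The likely number of missed events is small: at most 0.5 to 0.7 at the protocol's own rate, at most 2.0 to 2.4 at 9/244, and at most 0.2 to 0.3 hospitalised events. These bounds assume 54 to 66 baseline biopsies, one per patient, and every complication beginning before the dose; they fall if a cohort stops at stage 1. The timeline finding depends on none of these assumptions.

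This is worth changing because the omission concerns harm from a required research procedure and the remedy is cheap. It does not threaten the trial's efficacy conclusions.

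**What to change.** - In sections 4.10, 6.3 and 6.4, collect AEs and SAEs related to protocol-mandated procedures from registration or the first study-specific procedure. Keep the first dose as the start for all other events.
- Add a relatedness-to-procedure item to the AE case report form and to the Appendix F SAE form. Without it, the events that the new rule covers could not be identified.
- In section 12.3.2, add a listing of biopsy complications for every patient biopsied, dosed or not, separate from the drug-safety tables.

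Starting at registration is early enough for the biopsy, since footnote 1 of the calendar places biopsies after it. The cost is a few sentences, one new item on two forms, one listing and a few more records. The drug-safety analyses, sample size, power and alpha stay as they are.

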4.4.1 Entinostat (MS-275, SNDX-275)

4.3.1 Nivolumab (OPDIVO ®, BMS-936558; MDX-1106)

4.5 Supportive Care Guidelines and General Concomitant Medication

4.5.1 Supportive Care Guidelines

In general, concomitant medications and therapies deemed necessary for the supportive care and safety of the subject are allowed, provided their use is documented in the medical records and meets the dose modification guidelines outlined in **Section 5**.

The administration of any other therapies intended to treat the primary condition including chemotherapy and biologic agents is NOT permitted. Similarly, the use of other concurrent investigational drugs is not allowed.

Patients should receive appropriate supportive care measures as deemed necessary by the Investigator.

Blocking PD-1 function may permit the emergence of auto-reactive T cells and resultant clinical autoimmunity. Rash/pruritus, diarrhea/colitis, pneumonitis, hepatitis, and hypothyroidism were drug-related, presumptive autoimmune events noted in previous nivolumab studies.

All adverse events (AE) previously described in the Investigator's Brochures (IB) will be considered nivolumab-related AEs. For the purposes of this study, AE of unknown etiology, associated with drug exposure and consistent with an immune phenomenon, will be also considered nivolumab-related AE. Efforts should be made to rule out neoplastic, infectious, metabolic, toxin or other etiologic causes. Serological, immunological, and histological (biopsy) data should be used to support the diagnosis of an immune-mediated toxicity. Suspected nivolumab-related AEs must be documented on an AE or SAE CRF. Identification and treatment of nivolumab-related AEs can be found in **Appendix D**. Additional guidance can be found in the nivolumab IB.

Subjects who experience a grade 2 or higher nivolumab or entinostat-related AE should be discussed with the Principal Investigator (PI) and IND sponsor immediately

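### The Yes/No relatedness definitions in section 6.3 are stricter than the question they answer and leave events with plausible timing and an identified alternative cause without a category

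*Combined protocol and SAP*

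**What the plan says.** Section 6.3 requires the investigator to assess relatedness to entinostat and to nivolumab separately. It frames the assessment as a question: "Is there a reasonable possibility that the event may have been caused by one of the two drugs", or by the combination. Section 6.2.2 explains reasonable possibility, for IND safety reporting, as the existence of evidence suggesting a causal link. It does not require other causes to be excluded.

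Section 6.3 then gives two definitions for recording the answer:

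- *No* applies when the time course "rules out a causal relationship and another cause (concomitant drugs, therapies, complications, etc.) is suspected".
- *Yes* applies when the time course is "consistent with a causal relationship and no other cause (concomitant drugs, therapies, complications, etc.) can be identified".

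Other sections use different terms or rules:

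- Section 4.5.1: "All adverse events (AE) previously described in the Investigator's Brochures (IB) will be considered nivolumab-related AEs". It adds immune-type events of unknown cause as a further group.
- Section 6.1.2: "a nivolumab-related AE is defined as an AE of unknown etiology, associated with drug exposure and is consistent with an immune phenomenon". The sentence about brochure-listed events is absent.
- Section 6.7 (follow-up of adverse events) and the 7-day FDA report in section 6.10 refer to events possibly related to study drug. The written report in 6.10 refers to related events.
- The Appendix F form offers Unrelated and Related rows against three columns: entinostat, nivolumab and underlying disease.

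**The concern.** A binary classification should be mutually exclusive and exhaustive, and it should answer the question put to the investigator. Here *Yes* demands more than a reasonable possibility, and *No* is not its complement. Two investigators who agree on the facts of a case could record it differently, and neither would be breaking the text.

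Relatedness is used in several places:

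- Unacceptable toxicities in section 4.3 are limited to treatment-related events.
- Several nivolumab delay criteria in section 5.1 and discontinuation criteria in section 5.1.4 apply only to drug-related or treatment-related events.
- The FDA reports in section 6.10 depend on it.
- Section 12.3.2 tabulates adverse events by relationship to study drug.

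Section 6.12 sets no formal safety stopping rule and lists unacceptable toxicities among the data to be reviewed. Inconsistent attribution therefore enters safety monitoring through that count.

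**Working it through.** The plan states no figure on this point, so the check is logical.

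**1. Are the two definitions exhaustive?** Time course is taken as either ruling out the drug or consistent with it. Alternative cause is taken as none, suspected only, or identified, and an identified cause also counts as suspected. *No* = timing rules out AND a cause is suspected. *Yes* = timing consistent AND no cause is identified.

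| Time course | Alternative cause | Meets *No* | Meets *Yes* | Category |
|---|---|---|---|---|
| Rules out | None | no | no | **none** |
| Rules out | Suspected only | yes | no | No |
| Rules out | Identified | yes | no | No |
| Consistent | None | no | yes | Yes |
| Consistent | Suspected only | no | yes | Yes |
| Consistent | Identified | no | no | **none** |

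Two of six combinations have no category. The last row is the one that matters: the drug is plausible on timing and another cause has been found. The reasonable-possibility question can be answered yes for such an event, yet the definition of *Yes* refuses it. Two of six counts logical cells; it is not a proportion of events.

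**2. Can one study drug be the other's alternative cause?** The definitions list concomitant drugs among other causes, and attribution is made per drug. Section 5 says the two agents share fatigue, nausea and diarrhea and that drug causality will not always be clear. Read literally, nivolumab could be the identified alternative for entinostat and the reverse, so an event plausibly due to both would be *Yes* for neither. The text does not say that this is intended, and it does not exclude it.

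**3. Do the nivolumab rules agree?** Take a brochure-listed event with consistent timing and an identified non-drug cause.

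| Section | Result for nivolumab |
|---|---|
| 4.5.1 | Related, because listed |
| 6.1.2 | Outside the definition, because the cause is known |
| 6.3 | Neither *Yes* nor *No* |

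**4. How many events are affected?** The documents give no share of events with an identified alternative cause. The nearest figures are the event rates in section 6.1.1 from a lung cancer trial of erlotinib with entinostat or placebo. Placebo-to-entinostat ratios run from 2/14 = 0.14 (hypotension) to 18/31 = 0.58 (dyspnea). Over the ten listed events, the summed rates give 121/274 = 0.44. These events were listed because they were at least 10% more frequent on entinostat, they come from another disease, and they measure background rate, not whether a cause was identified. They cannot size the problem.

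**The case against.** The strongest reply is that the definitions are not meant to be applied mechanically and that other text limits the harm.

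- Section 6.3 follows the definitions with factors to weigh, such as disease course, concomitant medication and class effect. It also says "It will be left to the Investigator's clinical judgment to determine whether an AE is related", in the context of removal from treatment or study. This supports judgment, but gives no category in which to record an event that fails both definitions.
- Section 5 applies the most conservative approach to dose changes when causality is uncertain. That limits dosing consequences; it does not settle the tables, the unacceptable-toxicity count or the FDA test.
- Under section 6.4 all SAEs go to the IND sponsor and both companies whatever the causality. This stands, and that reporting line is unaffected.
- Section 6.2.2 supplies its own standard for IND safety reporting. This helps, but the investigator's assessment that feeds section 6.10 is still recorded under the 6.3 definitions.
- Section 6.1.2 largely repeats the second part of the 4.5.1 text, so the difference may be a drafting omission. That is plausible, and the two still need reconciling.

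Some stronger readings are tempting and should not be drawn:

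- A reader might infer that any possible alternative cause blocks *Yes*. Literally, only an identified cause does so.
- A reader might infer that the Appendix F form forces a choice between drug and disease. It has a separate underlying-disease column, so both can be recorded.
- A reader might infer that 6.1.2 makes all other events unrelated to nivolumab. It does not say so.

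**Conclusion.** The inconsistency is real and limited. Section 6.3 asks one question and records the answer by a stricter, non-exhaustive pair of definitions. An event with consistent timing and an identified alternative cause has no valid category, and the nivolumab rules in 4.5.1 and 6.1.2 differ. The consequence is missing or inconsistent attribution wherever relatedness is used.

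The documents do not support saying that most events in this population are affected, because no share is given or derivable. Nor do they support saying that the affected events count as unrelated: with consistent timing they fail *No* as well, although a two-option form may push them there in practice. Related-event rates are not themselves a secondary endpoint. Section 1.5.1 names CTCAE-graded adverse events, and relationship enters only as one example of a tabulation subgroup in 12.3.2. All-cause adverse event results and the primary response analysis are untouched.

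The conclusion rests on a literal reading of the two definitions, including the distinction between a suspected and an identified cause. The point about one study drug counting as the other's alternative cause is a possible reading, not a stated rule.

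**What to change.** Replace the two definitions in section 6.3 with one rule, applied to each drug separately. *Related*: there is a reasonable possibility that the drug caused the event, even if another cause is also possible. *Unrelated*: there is no reasonable possibility. Every event then falls in exactly one category, the standard is the one already used in 6.2.2 and in the 6.3 question, and the other study drug no longer blocks attribution.

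Align the terms in section 6.7, section 6.10 and the Appendix F form to this rule. Reconcile sections 4.5.1 and 6.1.2 with each other and with 6.3. Because relatedness feeds the criteria in sections 4.3, 5.1 and 5.1.4, the sponsor should settle which nivolumab attribution text governs; no view is taken here on those clinical criteria.

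The cost is wording in a few sections and one form. The reported related-event rate may be somewhat higher, since events with a competing cause can now be recorded as related. If events have already been classified under the current text, the report should say which definition each table uses.
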